7.1.4 Other Procedures

7.1.4.1 Withdrawal/Discontinuation

When a subject discontinues/withdraws prior to trial completion, all applicable activities scheduled for the final trial visit should be performed at the time of discontinuation. Any AEs which are present at the time of discontinuation/withdrawal should be followed in accordance with the safety requirements outlined in Section 7.2 - Assessing and Recording Adverse Events.

7.1.5 Visit Requirements

Visit requirements are outlined in Section 6.0 - Trial Flow Chart. Specific procedure-related details are provided above in Section 7.1 - Trial Procedures.

7.1.5.1 Post-Treatment Visits

7.1.5.1.1 Safety Follow-Up Visit

The mandatory Safety Follow-Up Visit should be conducted approximately 30 days after the last dose of trial treatment or before the initiation of a new anticancer treatment, whichever comes first. All AEs that occur prior to the Safety Follow-Up Visit should be recorded. Subjects with an AE of Grade > 1 will be followed until the resolution of the AE to Grade 0–1 or the beginning of a new antineoplastic therapy, whichever occurs first. SAEs that occur

within 90 days of EOT or before initiation of a new anticancer treatment should also be followed and recorded.

7.1.5.1.2 Follow-up Visits

Subjects who discontinue trial treatment for a reason other than disease progression will move into the Follow-Up Phase and should be assessed every 6 weeks (42 ± 7 days) by radiologic imaging to monitor disease status. After 1 year, the imaging time point will occur every 9 weeks (± 7 days). Every effort should be made to collect information regarding disease status until the start of new antineoplastic therapy, disease progression, death, or end of the study.

7.1.5.1.3 Survival Follow-up

Once a subject experiences confirmed disease progression or starts a new anticancer therapy, the subject moves into the Survival Follow-up Phase and should be contacted by telephone every 12 weeks to assess for survival status until death, withdrawal of consent, or the end of the study, whichever occurs first.

7.2 Assessing and Recording Adverse Events

An AE is defined as any untoward medical occurrence in a patient or clinical investigation subject administered a pharmaceutical product and which does not necessarily have to have a causal relationship with this treatment. An AE can, therefore, be any unfavorable and unintended sign (e.g., abnormal laboratory finding), symptom, or disease temporally associated with the use of a medicinal product or protocol-specified procedure, whether or not considered related to the medicinal product or protocol-specified procedure. Any worsening (i.e., any clinically significant adverse change in frequency and/or intensity) of a preexisting condition that is temporally associated with the study treatment is also an AE. Progression of the cancer under study is not considered an AE.

All AEs that occur after informed consent form signing must be reported by the investigator if they cause the subject to be excluded from the trial or are the result of a protocol-specified intervention, including but not limited to washout or discontinuation of usual therapy, diet, placebo treatment, or a procedure.

From the time of informed consent signing through 30 days following cessation of treatment, all AEs must be reported by the investigator. AE reporting will be performed according to 21 CFR 312.32. AEs will be recorded at each examination on the Adverse Event CRFs/worksheets. AEs (including lab abnormalities that constitute AEs) should be described using a diagnosis whenever possible, rather than individual underlying signs and symptoms. When a clear diagnosis cannot be identified, each sign or symptom should be reported as a separate AE. Conditions that were already present at the time of informed consent should be recorded in the Medical History page of the subject's CRF. The reporting timeframe for AEs meeting any serious criteria is described in section 7.2.3.1. The investigator will make every attempt to follow all subjects with non-SAEs for outcome.

AEs will not be collected for subjects during the prescreening period as long as that subject has not undergone any protocol-specified procedure or intervention. If the subject requires a blood draw, fresh tumor biopsy etc., the subject is first required to provide consent to the main study and AEs will be captured according to guidelines for standard AE reporting.

The occurrence of AEs should be sought by non-directive questioning of the patient at each study visit. AEs may also be detected when they are volunteered by the patient during or between visits or through physical examination, laboratory test, or other assessments. As far as possible, each AE should be evaluated to determine:

1. Severity grade (CTCAE Grade 1–4)
2. Duration (Start and end dates or if continuing at the Safety Follow-up Visit)
3. Relationship to the study treatment (Reasonable possibility that AE is related: No, Yes)
4. Action taken with respect to study or investigational treatment (none, dose adjusted, temporarily interrupted, permanently discontinued, hospitalized, unknown, not applicable)
5. Whether medication or therapy was given (no concomitant medication/non-drug therapy, concomitant medication/non-drug therapy)
6. Outcome (not recovered/not resolved, recovered/resolved, recovering/resolving, recovered/resolved with sequelae, fatal, unknown)
7. Whether it is serious, where a SAE is defined as in Section 7.2.3.1.

All AEs should be treated appropriately. Such treatment may include changes in study treatment including possible interruption or discontinuation, starting or stopping concomitant treatments, changes in the frequency or nature of assessments, hospitalization, or any other medically required intervention. Once an AE is detected, it should be followed until its resolution, and assessment should be made at each visit (or more frequently, if necessary) of any changes in severity, the suspected relationship to the study drug, the interventions required to treat it, and the outcome.

7.2.1 Definition of an Overdose for This Protocol and Reporting of Overdose to the Sponsor and to Merck

For purposes of this trial, an overdose of pembrolizumab will be defined as any dose of 1,000 mg or greater (≥ 5 times the indicated dose). No specific information is available on the treatment of pembrolizumab overdose. Appropriate supportive treatment should be provided if clinically indicated. In the event of overdose, the subject should be observed closely for signs of toxicity. Appropriate supportive treatment should be provided if clinically indicated.

If an AE(s) is associated with (“results from”) pembrolizumab overdose, the AE(s) is reported as a SAE, even if no other seriousness criteria are met.

If a dose of pembrolizumab meeting the protocol definition of overdose is taken without any associated clinical symptoms or abnormal laboratory results, the overdose is reported as a non-serious ECI, using the terminology “accidental or intentional overdose without adverse effect.”

For valacyclovir overdose, activated charcoal may be administered to aid in the removal of unabsorbed drug. General supportive measures are recommended. Acute renal failure and neurological symptoms, including confusion, hallucinations, agitation, decreased consciousness and coma, and nausea and vomiting may occur. Caution is required to prevent inadvertent overdose. Many of the reported cases involved renally impaired and geriatric patients receiving repeated overdoses due to lack of appropriate dosage reduction.

All reports of overdose with and without an AE must be reported within 24 hours to the Sponsor ([contact]; [contact]) and within 2 working days hours to Merck Global Safety (Attn: Worldwide Product Safety; [contact]).

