5.2.1.2 Dose Modification

Pembrolizumab: AEs (both non-serious and serious) associated with pembrolizumab exposure may represent an immunologic etiology. These AEs may occur shortly after the first dose or several months after the last treatment dose. Pembrolizumab must be withheld for drug-related toxicities and severe or life-threatening AEs as per Table 3 below. See Section 5.4 for supportive care guidelines, including use of corticosteroids.

Table 3 Dose Modification Guidelines for Pembrolizumab-Related AEs

Toxicity	Hold Treatment For Grade	Timing for Restarting Treatment	Treatment Discontinuation
Diarrhea/Colitis	2-3	Toxicity resolves to Grade 0-1	Toxicity does not resolve within 12 weeks of last dose or inability to reduce corticosteroid to 10 mg or less of prednisone or equivalent per day within 12 weeks
	4	Permanently discontinue	Permanently discontinue
Increased AST, ALT, or Bilirubin	2	Toxicity resolves to Grade 0-1	Toxicity does not resolve within 12 weeks of last dose
	3-4	Permanently discontinue (see exception below) ^a	Permanently discontinue
Type 1 Diabetes Mellitus (T1DM; if new onset) or Hyperglycemia	T1DM or 3-4	Hold pembrolizumab for new onset T1DM or Grade 3-4 hyperglycemia associated with evidence of beta cell failure	Resume pembrolizumab when patients are clinically and metabolically stable
Hypophysitis	2-4	Toxicity resolves to Grade 0-1. Therapy with pembrolizumab can be continued while endocrine replacement therapy is instituted	Toxicity does not resolve within 12 weeks of last dose or inability to reduce corticosteroid to 10 mg or less of prednisone or equivalent per day within 12 weeks
Hyperthyroidism	3	Toxicity resolves to Grade 0-1	Toxicity does not resolve within 12 weeks of last dose or inability to reduce corticosteroid to 10 mg or less of prednisone or equivalent per day within 12 weeks
	4	Permanently discontinue	Permanently discontinue
Hypothyroidism		Therapy with pembrolizumab can be continued while thyroid replacement therapy is instituted	Therapy with pembrolizumab can be continued while thyroid replacement therapy is instituted
Infusion Reaction	2 ^b	Toxicity resolves to Grade 0-1	Permanently discontinue if toxicity develops despite adequate premedication
	3-4	Permanently discontinue	Permanently discontinue
Pneumonitis	2	Toxicity resolves to Grade 0-1	Toxicity does not resolve within 12 weeks of last dose or inability to reduce corticosteroid to 10 mg or less of prednisone or equivalent per day within 12 weeks

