The End of Treatment and Follow-up visit procedures are listed in Section 7.1.5 (Visit Requirements). At the end of treatment (EOT), each subject will be followed for 30 days for AE monitoring (SAEs will be collected for 90 days after EOT as described in Section 7.2.3.1). Subjects who discontinue for reasons other than PD will have post-treatment follow-up for disease status until disease progression, initiating a non-study cancer treatment, withdrawing consent, or becoming lost to follow-up. After documented disease progression each subject will be followed by telephone for OS until death, withdrawal of consent, or the end of the study, whichever occurs first.

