6.0 TRIAL FLOW CHART

6.1 Trial Flow Chart

Visit	Screening ^a	Baseline ^b	V1	V2	V3	V4	V5	V6	V7	V8	V9	V10*	EOT	
Day	-28 to -1	-7 to -1	0±5	2±5	4±5	7±5	9±5	11±5	17±5	38±5	59±5	80*±5		
Informed Consent	X													
Inclusion/ Exclusion	X													
Demographics	X													
Medical History	X													
Physical Exam ^c	X		X						X	X	X	X	X	
Height	X													
Weight	X		X						X	X	X	X	X	
ECOG Performance Status	X		X						X	X	X	X	X	
12-Lead ECG and MUGA Scan or Echocardiogram ^d	X												X	
Concomitant Therapies	Continuous from screening period													
Hematology ^e	X		X						X	X	X	X	X	
Clinical Chemistry ^e	X		X						X	X	X	X	X	
Urinalysis ^f	X													
Serum Pregnancy (β-hCG) ^g	X													
Tumor Assessments (modified irRC and RECIST 1:1) ^h	X												X	
Brain MRI (NSCLC patients only) ⁱ	X													
Biopsy ^j			X						X					
Correlative Studies Blood Collection ^k	X								X		X			
AEs and SAEs	From informed consent signing up to 30 days after the last treatment dose^m													
ADV/HSV-tk Administration ^l			X											
Valacyclovir Administration ^l			X											
SBRT Administration ^l				X	X	X	X	X						
Pembrolizumab Administration ^l									X	X	X	X		

Abbreviations: AE = adverse event; ALT = alanine transaminase; ANC = absolute neutrophil count; aPTT = activated partial thromboplastin time; AST = aspartate transaminase; β -hCG, beta-human chorionic gonadotropin; BUN = blood urea nitrogen; CBC = complete blood count; CT = computed tomography; ECG = electrocardiogram; ECOG = Eastern Cooperative Oncology Group; EOT = end of treatment; GM-CSF = granulocyte macrophage colony-stimulating factor; IFN = interferon; IL = interleukin; INR = international normalized ratio; LDH = lactate dehydrogenase; MRI = magnetic resonance imaging; MUGA = multigated acquisition; Q3W = every 3 weeks; PD-1 = programmed death-1; PD-L1 = programmed death-ligand 1; PET = positron emission tomography; p.o. = orally; PT = prothrombin; RT = radiation therapy; SAE = serious adverse event; T3 = triiodothyronine; T4 = thyroxine; Th1 = T-helper; t.i.d. = three times daily; TIL = tumor-infiltrating lymphocyte; TNF = tumor necrosis factor; TSH = thyroid-stimulating hormone; vp = viral particles; WBC = white blood cell. A window of ± 5 days is allowed for visits and study assessments (except as otherwise specified).

a. Within 28 days prior to Day 0 of ADV/HSV-tk.

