tumors will be treated with a short course (5-8 fractions) of three-dimensional RT. SBRT and three-dimensional RT will be administered over 2 weeks from Day 2 to Day 16 of the study. Pembrolizumab at a dose of 200 mg will be intravenously infused over 30 min Q3W (\pm 1 day) starting on Day 17 (\pm 1 day) of the study and continuing until disease progression, unacceptable toxicity, or up to 24 months (35 cycles) in subjects without disease progression. All subjects who stop pembrolizumab treatment with complete response may be eligible for up to an additional 12 months (17 cycles) of pembrolizumab treatment if they progress after stopping pembrolizumab from the initial treatment phase. The subject must meet the conditions outlined in Section 5.2.3.

m. AEs and SAEs will be captured from the time of informed consent signing up to 30 days after the final dose of pembrolizumab. Study treatment-related SAEs and any study patient death occurring beyond 30 days after the last dose of pembrolizumab should also be reported.

*Patients will be treated until disease progression, unacceptable toxicity, or up to 24 months in subjects without disease progression.

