7.1.2.1 Adverse Event Monitoring

The investigator or qualified designee will assess each subject to evaluate for potential new or worsening AEs as specified in the Trial Flow Chart and more frequently if clinically indicated. Adverse experiences will be graded and recorded throughout the study and during the follow-up period according to the NCI CTCAE v4.03 (see Section 12.2). Toxicities will be characterized in terms of seriousness, causality, toxicity grading, and action taken with regard to trial treatment.

For both the TNBC and NSCLC cohorts, a safety run-in period will be implemented for the initial subjects enrolled onto the study. An initial cohort of 3 patients will be followed for toxicity through the first cycle of pembrolizumab. **The PI will submit a status update for the first 3 patients after each individual is enrolled onto this trial via a Reportable Event application.**

Please refer to Section 7.2 for detailed information regarding the assessment and recording of AEs and Section 8.0 for detailed information regarding the run-in cohorts.

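### The flow chart ends SAE capture 60 days short of the protocol's own 90-day rule, and the plan does not clearly require asking about new non-serious immune AEs after about Day 30

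*Combined protocol and SAP*

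**What the plan says.** The general rule in section 7.2 is "From the time of informed consent signing through 30 days following cessation of treatment, all AEs must be reported by the investigator". Section 5.6 agrees that after end of treatment "each subject will be followed for 30 days for AE monitoring", and adds that "SAEs will be collected for 90 days after EOT as described in Section 7.2.3.1". Section 7.2.3.1 gives the SAE rule in full: 90 days after treatment stops, shortened to 30 days if new anticancer therapy begins, whether or not the event is related. SAEs judged related are reportable at any time. Section 7.1.5.1.1 also uses 90 days for SAEs.

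The flow chart in section 6.1 differs. Its combined AE and SAE row reads "From informed consent signing up to 30 days after the last treatment dose", and footnote m says "AEs and SAEs will be captured from the time of informed consent signing up to 30 days after the final dose of pembrolizumab". After Day 30 the footnote keeps only treatment-related SAEs and deaths.

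On timing, section 5.2.1.2 says of pembrolizumab AEs with a possible immune cause, serious and non-serious alike: "These AEs may occur shortly after the first dose or several months after the last treatment dose".

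Two passages reach beyond Day 30 without a date. Section 7.1.2.1 says "Adverse experiences will be graded and recorded throughout the study and during the follow-up period", and section 7.2 asks for open AE questioning at every study visit. Neither says whether the post-treatment Follow-up Visits count. Section 7.1.5 sends the site back to the chart: "Visit requirements are outlined in Section 6.0 - Trial Flow Chart".

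**The concern.** There are two problems of different kinds.

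The first is a conflict between rules. Sites tend to work from a flow chart. This one gives a shorter SAE window than the text it summarises, so which events reach the sponsor depends on which page is followed.

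The second is a gap in ascertainment. The protocol itself warns of late immune events, including non-serious ones, but the only generally applicable dated window for non-serious AEs closes at about Day 30. The SAE rule does not fill this gap. Section 4.1.1.4.5 gives hypothyroidism in 7.2% of patients as an AE of special interest in KEYNOTE-001 and -002, against 0.2% as a drug-related SAE in the monotherapy trials. The bases differ and onset times are not given, so these are not late-onset rates. They do suggest that much immune toxicity is non-serious.

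Section 8.1 promises the frequency of all AEs. If sites read the follow-up text differently, late non-serious events enter those tables unevenly or not at all.

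**Working it through.** The plan states no figure to reproduce. The check sets the collection rules side by side, treating end of treatment, cessation of treatment and last dose as the same day.

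| Event type | Window after last dose | Section |
|---|---|---|
| All AEs | 30 days | 5.6, 6.1, 7.2 |
| All AEs, tied to the Safety Follow-Up Visit | about 30 days, or earlier if new therapy starts | 7.1.5.1.1 |
| All SAEs, per text | 90 days (30 if new therapy starts) | 7.2.3.1; 90 days also in 5.6 and 7.1.5.1.1 |
| All SAEs, per flow chart | 30 days | 6.1 row and footnote m |
| Related SAEs | no limit | 7.2.3.1; kept in footnote m |
| Deaths | kept after 30 days | footnote m |
| Events of clinical interest (ECIs), serious or not | 90 days (30 if new therapy starts) | 7.2.3.2 |
| AEs that interrupted or stopped treatment | weekly for 4 weeks, then every 4 weeks to resolution or stabilization | 5.2.1.2 |
| Toxicity after an interruption of more than 3 weeks | continued, no end date | 5.2.1.2 |

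**Conflict on SAEs.** Text minus chart: 90 − 30 = 60 days, that is Days 31-90. Related SAEs and deaths survive in footnote m. Once new therapy starts, section 7.2.3.1 also uses 30 days. What falls between the two rules is unrelated, non-fatal SAEs on Days 31-90 in patients without new anticancer therapy.

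**Gap on non-serious AEs.** Remove from the non-serious group everything with a rule beyond Day 30:

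- ECIs have 90 days, but the list has two items: pembrolizumab overdose without symptoms or abnormal results, and raised AST or ALT with raised bilirubin.
- AEs already detected are followed to resolution (7.2), with each grade change recorded (7.2.4).
- The toxicity follow-up in 5.2.1.2 mainly concerns AEs already present.
- Section 7.2 also has an undated clause on AEs that cause exclusion or result from a protocol-specified intervention. Its examples, such as washout and stopping usual therapy, read as aimed at the pre-treatment period.

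What remains is a new, non-serious, non-ECI immune AE that starts after about Day 30.

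**Later contacts.** Section 7.1.5.1.2 describes imaging for disease status every 6 weeks. Section 7.1.5.1.3 describes a telephone call for survival status every 12 weeks. Neither lists AE questions. If Follow-up Visits are counted from the last dose (an assumption), the first falls on Days 42 ± 7 = 35-49 and the second on Days 84 ± 7 = 77-91. Contacts inside the 90-day window therefore already exist for patients who stop for reasons other than progression.

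**Size.** One missed patient changes the rate of an individual event by 1/57 = 1.8 percentage points overall, 1/28 = 3.6 in TNBC and 1/29 = 3.4 in NSCLC, if that patient had not already had the event. This is the effect of a single patient and does not estimate how many are missed. The worst-grade-per-patient summary moves less, because a late event counts only if it exceeds the patient's earlier worst grade, and 83.0% to 100% of patients had some AE in the monotherapy trials (4.1.1.4.5).

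**The case against.** The best defence is that different windows for AEs and SAEs are a deliberate design choice. That stands. A reader might infer that the 30-day AE window contradicts section 5.2.1.2, but the sentence there introduces dose-modification guidance and sets no collection period.

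A reader might also infer that every rule for non-serious AEs ends at Day 30. The documents do not support that. Non-serious ECIs have 90 days, and one of them, the combined liver test elevation, could well be an immune event. Section 5.2.1.2 keeps some patients under toxicity follow-up. Serious events include other important medical events (7.2.3.1), so consequential late toxicity can be captured without hospitalization.

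Nor do the documents show that Follow-up Visits exclude AE questions. Sections 7.1.2.1 and 7.2 can be read to include them. That the chart, as extracted, ends at the EOT column proves little, since it also lacks a column for the mandatory Safety Follow-Up Visit. On the other side, section 7.2 asks whether an AE is continuing at the Safety Follow-up Visit, and section 5.3.1 limits later concomitant medication records to SAEs and ECIs. Both point to a record that closes at about Day 30. The wording is open to either reading, and that is the defect.

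Finally, a reader might infer a material bias in the secondary toxicity endpoint of section 3.2. This is speculative. That definition counts treatment-related deaths and hematological events of Grade 3 or higher. Grades 4 and 5, as described in section 7.2.4, point to SAE criteria, which leaves essentially late, non-serious Grade 3 hematological events.

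None of this answers the SAE conflict: footnote m and section 7.2.3.1 cannot both be followed.

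**Conclusion.** Two minor points hold.

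1. The flow-chart row and footnote m are wrong as written. They end general SAE capture 60 days before the rule in sections 5.6, 7.1.5.1.1 and 7.2.3.1. A site following the chart would lose unrelated, non-fatal SAEs on Days 31-90.
2. Outside ECIs and the follow-up in section 5.2.1.2, the dated window for non-serious AEs ends at about 30 days, and the plan does not make clear that later visits must ask about new ones. Late non-serious, non-ECI immune AEs may be under-counted in the section 8.1 tables.

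The number missed cannot be estimated, because the documents give no late-onset rate. The second point depends on how sites read two undated sentences; if all sites question patients at Follow-up Visits, little is lost among patients who attend them. Response rate, sample size and the run-in decision are not affected.

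**What to change.** **Flow chart.** Change the section 6.1 row and footnote m so that all SAEs run to 90 days after the last dose, or 30 days if new anticancer therapy starts, with related SAEs at any time, as in section 7.2.3.1.

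**Late AEs.** Keep 30 days for all AEs. In sections 5.6, 7.1.5.1.1 and 7.2, and in footnote m, add that new immune-mediated or treatment-related AEs of any seriousness are recorded through the same 90-day or 30-day window. State in sections 7.1.5.1.2 and 7.1.5.1.3 that patients are asked about them at the Follow-up Visits and survival calls already scheduled, and define the follow-up period in section 7.1.2.1 as this window. Calls need no re-timing if the question covers onset within the window and is asked until the first contact on or after Day 90.

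**Reporting.** In section 8.1, show these events as a separate late-onset line, so that the 30-day tables keep their meaning.

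**Cost.** Protocol wording and a few questions at existing contacts, with no new visits or tests. Recall error is the main weakness: a patient first called on Day 84 would next be called on Day 84 + 84 = 168, which is 78 days after the window closes. Asymptomatic laboratory changes would still be missed, since section 7.1.3 leaves thyroid tests after screening, and blood counts after end of treatment, to clinical indication. Ninety days may also be too short for the latest events. The reported toxicity rate may rise slightly.
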